All secondary and exploratory efficacy endpoints will be analyzed using the ITT population. Binary endpoints up to Week 28 will be analyzed based on the methods described for the primary endpoint. For change-from-baseline at Week 28 (continuous), secondary efficacy endpoints, MMRM model with treatment, visit (Weeks 4, 8,12,16,20,24,28), prior use of TNF-alpha inhibitors (yes/no), baseline body weight (≤90 kg or >90 kg), treatment-by-visit interaction as factors and corresponding baseline value as a covariate will be performed. Secondary and Exploratory efficacy endpoints obtained from

Endpoint	Statistical Analysis Methods
Change in total-fingernail NAPSI score from Baseline at Week 28.	Week 28 to Week 52 will be evaluated using summary statistics.
Change in patient-reported nail pain NRS score	summary statistics.
Clinician-assessed proportions of ViSENPsO category results at Week 28 compared between treatment groups.	
• The proportion of subjects achieving PASI 75, PASI 90, and PASI 100 at Week 28.	
• The proportion of subjects achieving a PGA-S score of "clear" or "almost clear" with at least 2-point reduction from Baseline at Week 28.	
Percentage change in total BSA involvement from Baseline at Week 28.	
• Change from Baseline in mNAPSI, NAPSI, Nail Pain NRS, BSA, PGA-S, s-PGA, PASI and the proportions of ViSENPsO category results at measured time points through Week 52.	
Change from Baseline in DLQI score (total and domain scores), NAPPA-QoL score, CGIC, CGIS, PGIC, PGIC-P, PGIS, and PGIS-P at measured time points through Week 52.	
The proportion of subjects with, at least, 30% decrease in Nail Pain NRS score from Baseline at Week 28 in subjects with a baseline nail pain NRS score of > 3	

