9.2.3 Analysis of Secondary Efficacy Endpoints

Binary endpoints

The following binary endpoints will be analyzed in a similar manner as the primary efficacy endpoint based on the analysis population specified in Table 5 in Section 9. A CMH test (rather than M-N methodology) will be used, stratified by prior use of TNF-alpha inhibitors (yes or no) and baseline body weight class (≤90 kg or >90 kg).

- ViSENPsO response at Week 28 (key secondary endpoint)
- ≥ 3-point decrease in Nail Pain NRS score from Baseline at Week 28 in subjects with baseline nail pain NRS score of ≥ 3
- mNAPSI90 at Week 28
- mNAPSI100 at Week 28
- NAPSI75 at Week 28
- NAPSI90 at Week 28
- NAPSI100 at Week 28
- PASI 75 at Week 28
- PASI 90 at Week 28
- PASI 100 at Week 28
- PGA-S response at Week 28

| Effe | ective Date: 10-AUG-2020 | Page | e 35 of 61 |
|------|--------------------------|------|------------|

• 30% decrease in Nail Pain NRS score from Baseline at Week 28 in subjects with baseline nail pain NRS score of ≥3

Continuous endpoints

Change from baseline to week 28 in total-fingernail mNAPSI and total-fingernail NAPSI scores (endpoints included in the hierarchical order of Section 4.5) during the double-blinded period will be analyzed based on the ITT population using MI to handle missing data.

MI procedures for continuous efficacy endpoint (total-fingernail mNAPSI and total-fingernail NAPSI scores):

Missing post-baseline total-fingernail mNAPSI or NAPSI scores through Week 28 will be imputed for the ITT separately for each treatment group using the Markov Chain Monte Carlo (MCMC) method. 50 copies of the dataset with monotonic missing pattern will be generated. For each of the 50 datasets, missing values at scheduled visits (Weeks 4, 8, 12, 16, 20, 24, and 28) will be imputed using a monotone regression model including treatment, presence of TNF-alpha inhibitors at baseline (yes or no), baseline body weight class (≤90 kg or >90 kg), baseline mNAPSI or NAPSI score, and mNAPSI or NAPSI scores at the previous scheduled visits. Change from baseline in mNAPSI or NAPSI score will be derived based on the imputed datasets.

Once imputations are made, the week 28 data of each of the 50 complete datasets will be

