analyzed using the ANCOVA model with treatment, randomization stratification factors (prior use of TNF-alpha inhibitors (yes or no), Baseline body weight class (≤90 kg or >90 kg)), and baseline value of the relevant endpoint included in the model, and the SAS MIANALYZE procedure will be used to generate valid statistical inferences by combining results from the 50 analyses using Rubin's formula.

NAPSI scores will be imputed using the same method as mNAPSI as stated above with replacement of mNAPSI with NAPSI in the imputation model.

Example SAS code is provided in Section 15.

Change from baseline to week 28 in other continuous endpoints (nail pain NRS and total BSA) during the double-blinded period will be analyzed based on the ITT population using OC.

All continuous endpoints will be analyzed using an analysis of covariance (ANCOVA) model with treatment, randomization stratification factors (prior use of TNF-alpha inhibitors (yes or no), Baseline body weight class (≤90 kg or >90 kg)), and baseline value of the relevant endpoint included in the model.

Additionally as supportive analysis, they will also be analyzed based on the ITT population for OC using a mixed model for repeated measures (MMRM) procedure that includes fixed effects for treatment, visit, treatment by visit interaction, prior use of TNF-alpha inhibitors

[figure not shown]
| Effective Date: 10-AUG-2020 | Page 36 of 61 |
|-----------------------------|---------------|

Effective Date: 10-AUG-2020

[figure not shown]
(yes or no), Baseline body weight class (≤90 kg or >90 kg), and baseline value of the relevant endpoint as a covariate, comparing the change from Baseline between tildrakizumab arm and placebo arm (refer to Section 15 15 for MMRM procedures).

- Mean change in nail pain NRS score from Baseline at Week 28
- Mean change in total-fingernail mNAPSI score from Baseline at Week 28
- Mean change in total-fingernail NAPSI score from Baseline at Week 28
- Mean percentage change in total BSA involvement from Baseline to Week 28

Treatment difference between tildrakizumab arm and placebo arm will be reported, along with the associated 95% CI and p-value.

Page 37 of 61

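### The supportive MMRM for the continuous secondary endpoints fits one baseline slope across Weeks 4 to 28, which may cost precision in its Week 28 treatment difference

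*SAP*

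**What the plan says.** SAP 9.2.3 gives the continuous secondary endpoints (nail pain NRS, mNAPSI, NAPSI and BSA) two models.

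- **Main analysis.** "All continuous endpoints will be analyzed using an analysis of covariance (ANCOVA) model with treatment, randomization stratification factors" and the baseline value. For mNAPSI and NAPSI this follows multiple imputation: "Once imputations are made, the week 28 data of each of the 50 complete datasets will be" analysed by that ANCOVA and combined. For nail pain NRS and BSA it uses observed cases.
- **Supportive analysis.** "Additionally as supportive analysis, they will also be analyzed based on the ITT population for OC using a mixed model" for repeated measures. The model "includes fixed effects for treatment, visit, treatment by visit interaction, prior use of TNF-alpha inhibitors", body weight class, and the "baseline value of the relevant endpoint as a covariate, comparing the change from Baseline between tildrakizumab arm and placebo arm". For code, the reader is told to "refer to Section 15 15 for MMRM procedures".

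Protocol Table 6 names only the MMRM for change from baseline at Week 28. It lists the visits as Weeks 4, 8, 12, 16, 20, 24 and 28 and ends the model with "treatment-by-visit interaction as factors and corresponding baseline value as a covariate will be performed".

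Neither document lists an interaction of baseline value with visit. SAP Section 1 says that the SAP takes precedence over the protocol on statistical matters. The text of SAP Section 15 is not in the copy available for this review.

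**The concern.** The treatment effect may differ at each of seven visits, but the regression of change on baseline may not. Soon after baseline a score is still close to where it started, so change depends little on baseline and the slope is near zero. If improvement then builds roughly in proportion to baseline severity, the slope becomes clearly negative by Week 28. A single fitted slope is pulled toward the early visits, where residual variance tends to be smallest. It then removes too little baseline variation at Week 28, the visit that matters.

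At stake is the width of the MMRM interval. A supportive model that uses seven visits should be at least as precise as the single-visit ANCOVA beside it. For nail pain NRS, where the main ANCOVA in 9.2.3 uses observed cases only, the MMRM is also the analysis in that section that draws on earlier visits of subjects who lack Week 28 data.

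**Working it through.** **The plan's own figure.** The documents give no SD, effect size or precision figure for any continuous endpoint. The only sample-size figure is for mNAPSI75 (protocol 9.2): 35% vs 10%, pooled Z-test, two-sided 0.05, 80% power.

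n = [1.96 × √(2 × 0.225 × 0.775) + 0.8416 × √(0.35 × 0.65 + 0.10 × 0.90)]² / 0.25² = (1.157 + 0.474)² / 0.0625 ≈ 42.6, so 43 per arm; 43 / 0.9 = 47.8, so 48 per arm.

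This reproduces the plan and does not depend on the MMRM.

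**Formula for the loss.** Let b28 be the true slope of change on baseline at Week 28, b* the fitted common slope, SDb the baseline SD, and s28 the Week 28 residual SD. Using b* in place of b28 leaves (b28 − b*)² × SDb² of unexplained variance, so

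SE ratio (common slope / by-visit slopes) ≈ √[1 + (b28 − b*)² × SDb² / s28²].

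**Simulation 1.** 48 per arm, seven visits, about 10% monotone dropout, unstructured covariance, 300 runs per row. Assumptions not in the documents: SDb = 1, residual SD rising over visits, residual correlation 0.8^lag, slope moving linearly from Week 4 to Week 28. The stratification factors were left out of all models.

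| Slope, Week 4 to Week 28 | s28 | Fitted b* | Ratio by formula | Simulated ratio | Common-slope SE / ANCOVA SE |
|---|---|---|---|---|---|
| −0.5 to −0.5 | 0.9 | −0.502 | 1.000 | 0.997 | 0.1911 / 0.1946 = 0.98 |
| −0.3 to −0.5 | 0.9 | −0.336 | 1.017 | 1.015 | 0.1946 / 0.1946 = 1.00 |
| −0.1 to −0.5 | 0.9 | −0.135 | 1.079 | 1.078 | 0.2067 / 0.1946 = 1.06 |
| −0.1 to −0.8 | 0.8 | −0.188 | 1.259 | 1.257 | 0.2142 / 0.1730 = 1.24 |
| −0.05 to −0.9 (extreme) | 0.7 | −0.110 | 1.508 | 1.499 | 0.2236 / 0.1513 = 1.48 |

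Third row as an example: √[1 + (0.5 − 0.1345)² / 0.81] = √1.165 = 1.079. The fitted slope sits near the Week 4 value, as the mechanism predicts. Bias of the common-slope estimate stayed below 0.01 baseline SD. The Week 28 ANCOVA SE was 1.015 times the by-visit MMRM SE in every row.

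**Simulation 2.** Same n, complete data, equal SD at every visit, so slope = correlation with baseline − 1; 600 runs. Ratio of mean SEs as the correlation falls from Week 4 to Week 28:

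- 0.9 to 0.5: 3.897 / 3.568 = 1.09
- 0.9 to 0.4: 4.268 / 3.778 = 1.13
- 0.9 to 0.3: 4.728 / 3.917 = 1.21
- 0.85 to 0.5: 3.726 / 3.553 = 1.05
- 0.8 to 0.6: 3.352 / 3.303 = 1.015
- 0.75 to 0.5: 3.603 / 3.552 = 1.014

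**Simulation 3, tied to the plan's response assumption.** mNAPSI improvement proportional to baseline, building linearly, calibrated to 35% vs 10% reaching 75% improvement at Week 28, baseline at least 20. Assumed: between-subject SD of proportional improvement 0.25 to 0.45, baseline SD about 12 or 18, visit noise SD 4 or 8. Mean slopes moved from between −0.04 and −0.08 at Week 4 to between −0.34 and −0.54 at Week 28. Across 12 scenarios the common-slope SE was 1.5% to 22% larger than the by-visit SE.

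**The case against.** The strongest reply is that this does not touch what the trial will conclude. The SAP makes ANCOVA the main analysis and the MMRM an addition, and the SAP takes precedence over the protocol. The mNAPSI and NAPSI changes that 9.2.3 places in the testing hierarchy are analysed by imputation and ANCOVA. That ANCOVA fits its own Week 28 slope. All of this stands.

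It is also true that the slopes are assumed. No document figure shows that they differ between visits, and with equal slopes nothing is lost. With modest drift (−0.3 to −0.5) the common-slope MMRM was as precise as the ANCOVA. The Section 15 code might already contain the term. For BSA the response is percentage change; if improvement is proportional to baseline, the slope of percentage change is near zero at every visit and little is lost.

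A reader might infer more than the documents support:

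- **That the trial's Week 28 treatment difference is imprecise.** Only the supportive estimate is affected under the SAP. The criticism would reach a main analysis only if protocol Table 6 stood alone.
- **That the trial needs more subjects.** The sample size rests on the binary mNAPSI75 endpoint, which this model does not enter.
- **That a wider MMRM interval would count as failure to confirm.** No rule in the available text says so.

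What the reply does not remove is the wording. Both documents list a single baseline covariate beside a treatment-by-visit term, and the plan's own 35% vs 10% assumption makes a steepening mNAPSI slope plausible.

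**Conclusion.** The point holds as a minor efficiency issue in a supportive analysis. As worded, the MMRM can give a less precise Week 28 difference than the same data allow, and less precise than the ANCOVA it accompanies. The size is conditional: no loss with equal slopes, and about 2% to 20% in SE when slopes steepen to around −0.3 to −0.7 by Week 28. Larger losses (26% and 50%) appeared only when the Week 28 slope was set at −0.8 or −0.9, and they should not be taken as expected values. The case is plausible for mNAPSI, NAPSI and nail pain NRS and weak for BSA. The simulation showed no material bias, and model SEs were close to the empirical SDs, so the analysis as written remains valid.

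**What to change.** Before unblinding:

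1. In SAP 9.2.3, add the interaction of baseline value with visit to the MMRM fixed effects and leave the rest of the model unchanged.
2. Check that the Section 15 code matches. If it already has the term, only the wording of 9.2.3 needs correcting.
3. Align protocol Table 6, or record the difference in the SAP.

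The cost is six extra fixed-effect parameters (seven visit slopes instead of one), one line of text and no new data. If slopes prove equal, the added term costs essentially nothing: the SE ratio was 0.997.

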9.4 Other/Exploratory Efficacy Analysis

9.4.1 Other/Exploratory Efficacy Endpoints

Other efficacy endpoints are described in Section 2.3.3.

Key definitions for other efficacy endpoints are described as following:

DLQI (Dermatology Life Quality Index)

The DLQI is a 10-question questionnaire to assess treatment response on the subject's quality of life, covering 6 domains: Symptoms and Feelings, Daily Activities, Leisure, Work and School, Personal Relationships, and Treatment. Each question is scored from 0 to 3, giving a possible score range from 0 (no impact) to 30 (maximum impact).

Detailed scoring algorithms for DLQI are provided in Appendix 2 DLQI Scoring.

NAPPA-QoL (Nail Assessment in Psoriasis and Psoriatic Arthritis Quality of Life)

NAPPA-QoL is a 20-item questionnaire describing the QoL with nail psoriasis on the hands and/or feet over the past week. Answers are given in Likert scales from 0 to 4. Factor analysis revealed three scales named 'Signs' (nail status), 'Stigma' (nail impact: stigma and emotional status), and 'Everyday life' (nail impact: everyday life).

Detailed scoring algorithms for NAPPA-QoL are provided in Appendix 3 NAPPA-QoL Scoring.

CGIC (Clinician Global Impression of Change)

The CIGC is a simple questionnaire that reflects a clinician's belief about the efficacy of treatment. The CGIC describes the overall change in patient's nail psoriasis since he/she started taking the study medication: much better, a little better, no change, a little worse, much worse.

CGIS (Clinician Global Impression of Severity)

| _ | |
|-----------------------------|---------------|
| Effective Date: 10-AUG-2020 | Page 39 of 61 |

CIGS is a global index that is used by clinicians to rate the severity of a specific condition in patients (a single-state scale): none, mild, moderate, severe, very severe.

PGIC (Patient Global Impression of Change)

PGIC is a simple questionnaire that reflects a patient's belief about the efficacy of treatment: much better, a little better, no change, a little worse, much worse.

PGIC-P (Patient Global Impression of Change for pain)

PGIC-P is a simple questionnaire that describes the overall change in nail pain: much better, a little better, no change, a little worse, much worse.

PGIS (Patient Global Impression of Severity)

The Patient Global Impression of Severity is a global index used to rate the severity of a specific condition (a single-state scale): none, mild, moderate, severe, very severe.

PCIS-P (Patient Global Impression of Severity for pain)

PGIS-P to evaluate the intensity of nail pain at the post-baseline visits wherein PGIS will also be recorded: none, mild, moderate, severe, very severe.

Inter-rater reliability of the ViSENPsO Scale

For a subset at selected sites, the ViSENPsO will be administered to the same patient by two internal assessors at the Baseline and EoT visits. For this, a psychometric analysis plan will be created, which will detail all the exploratory and correlation analyses between the newly developed ViSENPsO Scale and clinical variables and will be presented separately.

9.4.2 Analysis of Other/Exploratory Efficacy Endpoints

All exploratory endpoints will be summarized using the ITT population using descriptive statistics for all scheduled visits through Week 52.

In addition, subject achieving mNAPSI75 and subjects achieving ViSENPsO response by visit will also be analyzed using the same method as primary/key secondary efficacy endpoints in an exploratory manner.

10 SAFETY ENDPOINTS

The safety and tolerability of the study drugs are determined by reported adverse events (AEs), physical examinations, electrocardiogram results (ECGs), vital signs, and laboratory test results (Hematology, Biochemistry, and Urinalysis), and Columbia-Suicide Severity Rating Scale (C-SSRS).

| Effective Date: 10-AUG-2020 | Page 40 of 61 |
|-----------------------------|---------------|

All safety summaries will be based on the entire SAF.

Following reporting of Week 28 results, a group comprising formerly placebo-treated subjects who migrate to tildrakizumab 100 mg for the remainder of the study will be identified for reporting at the end of the study.

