3.3 Analysis Time points

Unless specified otherwise, efficacy and safety endpoints will be analyzed according to their scheduled study visits; unscheduled and early termination visits will be mapped to windowed analysis visits defined by actual study day as in table 1.1 below. If there is no evaluation available from the scheduled study visit, and more than one non-missing evaluation is assigned to an analysis window, the evaluation closest to the target day will be used for the analysis. If the two visits are equidistant from the target day, the earlier visit will be used. For early terminated patients, Part 3 is to start the day of last assessment after the last injection plus 28 days.

The following analysis visit windows will apply:

Table 1.1 Analysis Visit Windows

For: ViSENPsO, NAPSI, mNAPSI, PGA-S, BSA, PASI, and C-SSRS

| Derived Visit | Week | Target Day | Analysis Window |
|---|------|------------|-----------------|
| Part 1: Double-blind Placebo-controlled | | | |

| Effective Date: 10-AUG-2020 | Page 17 of 61 |
|-----------------------------|---------------|

| | _ |
|--|---|
| | |

| _ | |
|-----------------------------|---------------|
| Effective Date: 10-AUG-2020 | Page 18 of 61 |

In particular, NRS pain score will be recorded daily in patient diary for the 7 days leading up to each scheduled visit. The analysis visit for NRS will be assigned the same as for the subsequent visit according to Table 1.1, ie, as 7 consecutive days prior to that visit. In the event of a missed visit, the available NRS scores will be mapped to an analysis visit according to Table 1.1, using the last diary entry date as anchor. Any NRS entries outside of the 7-day window will be excluded from the calculation of average NRS. At least 4 out of the 7 daily records are required to calculation of average.

All other assessments (ECG, laboratory data) will be analyzed according to the assigned (nominal) visit unless otherwise specified.

[figure not shown]
For any events/assessments on or after the first administration of study drug, study day is calculated as: event/assessment date – date of first administration of study drug + 1. As such, Day 1 is defined as the date of first administration of study drug.

For any events/assessments before the first administration date, study day is calculated as event/assessment date – date of first administration of study drug.

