3.5 Analysis Populations

The following analysis sets will be used in the study:

Intent-to-Treat (ITT) Set: All randomized subjects regardless of the treatment actually received.

Safety Analysis Set (SAF): All randomized subjects who have received at least 1 dose of study treatment.

Per Protocol Set (PPS): All subjects in the ITT population who have completed the 28-week placebo-controlled treatment without any major protocol deviation that could impact data interpretability for the primary and key secondary efficacy endpoints.

The composition of the PPS will be determined in blind review of the database conducted prior to the primary analysis at Week 28. Prior to breaking the blind at Week 28, alternate criteria for exclusion from the PPS may be applied to accommodate unforeseen events that occurred during the conduct of the study.

The primary efficacy and key secondary endpoints will be analyzed using the ITT Set as well as the PPS for supportive analyses.

Safety endpoints will be analyzed descriptively based on the SAF, and subjects will be summarized based on the actual treatment they received.

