10.1 Adverse Events

The incidence of treatment-emergent AEs (TEAE) will be summarized and tabulated by treatment group, MedDRA (Version 24.0 or higher) System Organ Class (SOC) and Preferred Term (PT). A TEAE is defined as an AE that first occurred or worsened in severity after the first administration of study treatment.

AEs that cannot be definitely determined as occurring prior to first study drug administration will be counted as TEAEs unless either the partial start date or a partial or complete end date indicates the AE as occurring prior to treatment. Partial dates entered in the AE form will be imputed for the purposes of determining whether the record is a treatment emergent adverse event based on the following:

- AE onset dates with missing day and non-missing month will be assumed to occur on the first day of the non-missing month, except for AEs occurring in the month and year of first dosing of study drug, in which case the date will be imputed using the date of first dosing of study drug.
- AE onset dates with missing day and month will be assumed to occur on the first day
 of the non-missing year (i.e., January 1), except for AEs occurring in the year of first
 dosing of the study drug, in which case the date will be imputed using the date of the
 first dosing of study drug.
- Partial or missing AE resolution dates will not be imputed.

Several occurrences of the same AE in one subject will be counted once at the worst severity grade. If severity is missing, the event will be classified as of unknown severity for analysis and summarization.

The relationship of each AE to the study drug will be grouped as related (definitely, probably, possibly related) or unrelated (unlikely to be related, unrelated). Several occurrences of the same AE in one subject will be counted once and the one with the closest relationship to study medication will be counted. If an AE is missing the relationship to study medication, the event will be assumed to be related to study drug for analysis and summarization.

AEs will be further categorized by Study Part (1, 2, 3) as follows:

- Part 1 (Day 1 to Week 28): includes all AEs that first occurred or worsened in severity after the first study medication administration, but do not start after the Week 28 study medication administration.
- Part 2 and 3 (Week 28 and beyond): includes all AEs that first occurred or worsened in severity after the Week 28 injection. These will be performed for the final analyses.

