| Effective Date: 10-AUG-2020 | Page 41 of 61 |
|-----------------------------|---------------|

Non-TEAEs will be listed only and will not be included for analysis and summarization.

All AEs will be presented in a by-treatment and by-subject listing for Part 1, detailing the verbatim term, SOC, PT, injection site reaction or not, related to study indication or not, start date, stop date, time since most recent dose of IP, severity, outcome, relationship to study drug, action taken regarding study drug, other action taken, seriousness and criteria for seriousness. Serious AEs (SAEs) and TEAEs leading to study medication discontinuation, AEs of Special Interest (AESI), and events of clinical interest (ECI) will also be presented in separate listings.

An AE profile for the SAF will be provided for Part 1, Parts 2 and 3, and overall, which summarizes the subject incidence, by treatment received for the following information:

- Any TEAEs;
- Drug-related TEAEs;
- Any TEAEs with an outcome of death;
- Treatment-emergent SAEs;
- Drug-related treatment-emergent SAEs;
- TEAEs leading to discontinuation of study medication;
- Drug-related TEAEs leading to discontinuation of study medication;
- Any AEs of special interest, including:
 - Injection site reactions
 - Severe infections
 - o Malignancies (excluding carcinoma in situ of the cervix).
 - Non-melanoma skin cancer
 - Melanoma skin cancer
 - Major Adverse Cardiovascular Events (MACE)
 - Study treatment-related hypersensitivity reactions (e.g., anaphylaxis, urticaria, angioedema, etc.).

| Effective Date: 10-AUG-2020 | Page 42 of 61 |
|-----------------------------|---------------|

Study treatment-related hypersensitivity reactions will be identified based on Sponsor review of treatment-blinded listings of AE preferred terms prior to declaration of the IA DB freeze.

The number and percentage of subjects with TEAEs will be summarized for each treatment arm and/or in total by SOC and PT. Drug-related TEAEs, TEAEs leading to discontinuation of study drug, drug-related TEAEs leading to discontinuation of study drug, treatment-emergent SAEs, and drug-related treatment-emergent SAEs, AESI and ECI will be summarized in the same manner. For these summaries, subjects with multiple AEs will be counted only once per SOC and PT.

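### Read literally, the SAP reports Parts 2-3 adverse event incidence on the entire SAF but counts only events after the Week 28 injection, which modestly dilutes rates in the arm randomised to tildrakizumab

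*SAP*

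**What the plan says.** **Denominator.** SAP Section 10: "All safety summaries will be based on the entire SAF". Section 3.5 defines the SAF as: "All randomized subjects who have received at least 1 dose of study treatment". Reaching Week 28 is not required. Section 10.1 names the same set for the tables at issue: "An AE profile for the SAF will be provided for Part 1, Parts 2 and 3, and overall". The entries are subject incidences by treatment received.

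**Numerator.** In Section 10.1 the Parts 2-3 category "includes all AEs that first occurred or worsened in severity after the Week 28 injection". The Part 1 category takes treatment-emergent events that "but do not start after the Week 28 study medication administration".

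**Switch group.** For end-of-study reporting, Section 10 says that "a group comprising formerly placebo-treated subjects who migrate to tildrakizumab 100 mg for the remainder of the study will be identified". It does not state a denominator for that group.

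**A different boundary in Section 3.3.** The analysis-time-point section says: "For early terminated patients, Part 3 is to start the day of last assessment after the last injection plus 28 days". This gives subjects who stop early a Part 3 period that does not depend on a Week 28 injection.

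**Subjects without a Week 28 injection are expected.** Subjects may leave in Part 1, may take early escape at Week 16, or are discontinued at Week 28 for worsening (SAP Section 2.1). Protocol Section 9.5 makes explicit provision for them with a Day 210 cut-off for the Week 28 analysis. SAP Section 10.1 has no counterpart.

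**The concern.** An incidence proportion should have in its denominator only subjects who could have entered the numerator. Here one rule sets the denominator (any dose at any time) and another sets the numerator (onset or worsening after the Week 28 injection). A subject dosed in Part 1 only satisfies the first and cannot satisfy the second, however many events occur during the 20-week safety follow-up. Under the Section 10.1 boundary those follow-up events go to Part 1 instead.

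At stake are the Parts 2-3 percentages for treatment-emergent events, serious events and events of special interest in the arm with the longest tildrakizumab exposure. They would be understated. They could also look lower than those of the switch group at equal risk, because by definition every member of the switch group went on to tildrakizumab. The issue is who is counted, not how long each subject is followed.

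**Working it through.** **Inputs**

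- Planned size: 43 evaluable and 48 randomised per arm, with dropout of up to 10% (Protocol Sections 1.1 and 9.2).
- Parts 2-3 numerator and denominator rules: SAP Sections 10 and 10.1.
- Assumptions: all 48 randomised subjects per arm receive a first dose, so the SAF is 48; the share not dosed at Week 28 equals the planned dropout. The documents give no forecast of the latter, so a range is shown.

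**Step 1. Reproduce the plan's figures.** For 35% versus 10%, two-sided alpha 0.05, 80% power and a pooled z-test without continuity correction:

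n = [1.960 × √(2 × 0.225 × 0.775) + 0.842 × √(0.35 × 0.65 + 0.10 × 0.90)]² / 0.25² = 42.6, rounded up to 43 per arm.

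Then 43 / 0.90 = 47.8, rounded up to 48. Power at 43 per arm is 80.4%. The stated 43 and 48 are reproduced. The documents state no Parts 2-3 event rate or denominator count to check.

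**Step 2. Dilution factor.** Under the Section 10.1 rule, let m be the SAF subjects in the arm given the Week 28 injection and N all SAF subjects in the arm:

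shown rate = rate among dosed subjects × m / N.

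At planned dropout, m / N = 43 / 48 = 0.896.

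| Not dosed at Week 28 (assumed) | m of 48 | Factor | True 5% | True 10% | True 20% | True 40% |
|---|---|---|---|---|---|---|
| 5% | 46 | 0.958 | 4.8% | 9.6% | 19.2% | 38.3% |
| 10% (planned dropout) | 43 | 0.896 | 4.5% | 9.0% | 17.9% | 35.8% |
| 20% | 38 | 0.792 | 4.0% | 7.9% | 15.8% | 31.7% |
| 30% | 34 | 0.708 | 3.5% | 7.1% | 14.2% | 28.3% |

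A larger trial does not remove the effect. At the cap of 282 subjects (141 per arm) and 10% loss, the factor is 127 / 141 = 0.901.

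**Step 3. If the Section 3.3 boundary governed adverse events.** Some or all of the 5 subjects without a Week 28 injection could then contribute Part 3 events. With 0 to 5 of them able to contribute, the factor runs from 43 / 48 = 0.896 to 48 / 48 = 1.0.

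**Step 4. Against the switch group.** If that group is reported on its 43 migrants and the other arm on its 48 SAF subjects, equal event counts give rates that differ by a factor of 48 / 43 = 1.12. This holds only if the switch group's denominator is its own members, which the wording implies but does not state.

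**The case against.** The strongest reply is that Section 10 names an analysis set and does not set a column total for each period.

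- **Treatment received.** Section 10.1 presents its tables by treatment received, including the severity, relationship and common-event tables by study part. A subject with no injection from Week 28 onward received nothing in Parts 2-3 and might be left out of every column. That is a sensible reading, but it does not displace the explicit reference to the entire SAF or its repetition for the Parts 2-3 profile.
- **Mock-ups.** SAP Section 14 says that some table-specific rules are in the mock-ups, and the table list and shells are not in the available text. A proper denominator may be stated there. This stands as a limit on certainty.
- **Section 3.3.** A reader might infer that subjects without a Week 28 injection can never count towards Parts 2-3. The documents do not support that without qualification, because Section 3.3 gives early terminators a Part 3 start of their own. Section 3.3 deals mainly with visit windows and Section 10.1 is the specific adverse event rule, so the latter more naturally governs. Still, the two conflict, and which governs should be stated.
- **Switch-group contrast.** A reader might also infer a planned comparison with unequal denominators. No such comparison is specified, no denominator is stated for the switch group, and the two groups differ in dosing weeks and prior exposure.
- **Size.** The 10% is an upper planning figure for evaluability at the primary endpoint, not a forecast of missed Week 28 injections. Disposition is reported by study part (Section 6.2), so a careful reader could approximate the undiluted rate. Both remarks are fair and limit the weight of the point.

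**Conclusion.** The point holds as a literal reading of SAP Sections 10 and 10.1: the Parts 2-3 numerator and denominator cover different subjects in the arm randomised to tildrakizumab. With 10% not dosed at Week 28, shown rates are about 10% too low in relative terms, or about 2 percentage points at a true 20%. With 20% not dosed, a true 20% shows as about 16%. The size rests on the assumed share without a Week 28 injection and on the Section 10.1 rule governing. Under Section 3.3 the dilution is smaller and may vanish.

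Safety is analysed descriptively, so no hypothesis test is affected. Nor do these percentages make up all the trial's tildrakizumab data after Week 28, as a reader might infer, because the switch group also receives the drug from Week 28. It remains worth correcting: these tables carry the later safety experience of the longest-exposed arm, and the error runs towards understatement.

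**What to change.** 1. In SAP Sections 10 and 10.1, define the denominator of all Parts 2-3 adverse event tables as SAF subjects who received the Week 28 injection, shown by treatment sequence (tildrakizumab throughout; placebo then tildrakizumab). Apply it to the profile, SOC and PT, severity, relationship and common-event tables.
2. Keep the entire SAF for Part 1 and overall tables.
3. Reconcile Section 10.1 with Section 3.3 by stating in which table the follow-up events of subjects without a Week 28 injection are counted, so that numerator and denominator cover the same subjects in each table. Without this, changing the denominator alone leaves the place of those events unclear.
4. Check that the table mock-ups carry the same denominators.

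The cost is SAP wording and one population flag. The stated Parts 2-3 rates will be slightly higher.
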